How Yttrium 90 integrates into current treatment paradigms for primary and secondary cancers will depend on our ability to stratify patients at risk for liver related complications based on relevant functional evaluation of the liver remnant prior to treatment. By assessing global and regional liver function and volume before and after Y-90 therapy, we will be able to determine the potential correlation between Y-90 radiation dose to the background liver and potential radioembolization induced liver damage (REILD). A broader understanding of the relationship between Y-90 and REILD will allow us to develop a safer pre-treatment assessment model for avoidance of and prediction of REILD increasing patient safety and improving Y-90 outcomes.

Measuring liver function is a challenging clinical issue due to its complex microsomal, cytosolic, excretory and synthetic functions.¹ A combination of clinical and laboratory findings are used in daily practice for liver assessment. However, these are not specific or accurate enough to use alone for detection of Y-90 induced regional liver function changes. This is partially due to the liver's unique ability to regenerate after an injury, thereby masking measurable changes.

Additionally, laboratory tests only measure by-products of the liver's multiple complex functions. These tests are dependent on substrate availability and volume of its distribution which are unknown and variable and therefore limit their use. Clinical findings also suffer from wide variances in assessment and may be affected by other underlying conditions. If a good measuring tool for liver function were established, we would not need to measure so many lab values, clinical parameters, and clinical findings in addition to using multiple various scoring systems such as MELD and Childs-Pugh.

Quantitative accurate functional testing in general requires administration of a known amount of substrate that the measured function specifically consumes or traps. Two existing techniques that fulfill these criteria for liver function assessment are Indo Cyanine Green clearance (ICG) and a quantitative HIDA scan, a nuclear medicine scan.

ICG clearance is a widely used and validated method for measuring global, but not regional, liver function. Therefore, as both global and regional liver function need to be measured in this study, ICG will not be useful.

The HIDA technique was selected for this study as the gold standard for global and regional liver function. This scan involves administration of a known amount of a specific radiotracer, which is only extracted from the blood pool by the liver. An accurate measurement of liver function can be made by measuring liver and blood pool activity over a set time period using a gamma camera. This technique has been compared to the ICG method and has been found to be similar both in animal and human models.^{2,3} It uniquely provides measurement of both global and regional function, and also provides images that can be analyzed unlike the ICG test.

Like any known and used medical test, the HIDA scan has false positives and negatives. However, based on the literature showing good results, we are confident that it is a good choice. Additionally, our preference for HIDA scans is based on our own experience with this technique here at IU. We have been using it here for the past 5 years and have developed and validated specific software, learned how to interpret these studies with confidence, and published on it.⁴ It has also shown excellent results for liver surgery planning. Another imaging technique to assess for liver injury is CT scanning. Interval change in organ size can be used as a surrogate for liver radiation injury, with loss of size reflecting degree of damage. However, changes in organ size are much slower to occur and less specific than functional changes as measured by the HIDA scan. As part of routine clinical care, patients undergo multiple scans before and after their Y-90 therapy. We intend to measure global and regional liver volumes through routine CT scans on patients up to 12 months after their therapy to look for slowly occurring changes.

2. Rationale

The primary question of interest is quantifying the relationship between Y-90 liver therapy and liver damage. Little is known on this subject. Present assumptions and calculations of Y-90 administration are based on surgical lobar hepatectomies and external radiation beam therapies. We hope that by using a functional model of the liver, we can improve this important knowledge gap.

We will be enrolling patients planning to receive Y-90 therapy for the treatment of liver malignancies. The diagnosis of a primary liver cancer, hepatocellular carcinoma (HCC), is usually made by a combination of specific imaging findings and clinical criteria; only rarely is a confirmatory biopsy performed. This is due to the high accuracy of the present diagnostic model and the significant risk of biopsy and tumor seeding.

Y-90 therapy involves administering radioactive particles to liver tumors by placing a catheter in a hepatic artery supplying the tumor using angiographic techniques and injection of these particles.

Y-90 PET/CT imaging has been established as a method to validate and quantitate distribution of Yttrium after Y-90 administration. The post Y-90 therapy PET/CT images provide an imaging

distribution of the Y-90, which is essential for validation of administered versus planned dose to the liver lesion and background liver.

If we can compare the Y-90 distribution to estimate background liver radiation distribution and dose (generated by the Y-90 PET/CT scan) combined with the global and regional function map (generated by the HIDA scan performed before and after therapy), then we will be assuming that the difference pre and post therapy in global and regional function can be ascribed to the Y-90 administration. We will also analyze the CT sets performed before and after therapy and correlate the imaging results collected with clinical findings such as ascites/encephalopathy and routine serological markers (bilirubin, albumin, INR, etc.). With this information, we will have the potential to establish whether there is a relationship between Y-90 distribution to non-tumoral (normal) hepatic parenchyma and the incidence and severity of REILD. This would have the potential to improve selection criteria and outcomes in populations selected for Y-90 therapy in the future.

3. Objectives

3.1 Primary Objective:

1. Determine the difference in regional liver function between pre and 3 months post Yttrium 90 delivery using the HIDA functional imaging scans.

3.2 Secondary Objectives:

1. Determine the difference in global liver function between pre and 3 months post Yttrium 90 delivery using the HIDA functional imaging scans.
2. Determine the correlation between the differences in liver function (both regional and global) with the Y 90 dose provided.

4. Eligibility Criteria

4.1 Inclusion Criteria:

1. Subjects must have the ability to understand and the willingness to sign a written informed consent document.
2. Subjects must be ≥ 18 years of age at the time of signing informed consent.
3. Subjects must have a diagnosis of hepatocellular carcinoma (HCC) and a treatment plan to undergo radioembolization therapy with Y-90 at Indiana University Health Hospital.

4. Subjects must be willing and able to comply with all procedures and visits required for this protocol (pre-treatment, during treatment, and post-treatment).

4.2 Exclusion Criteria:

1. Subjects who have contraindications for receiving Y-90 therapy and any routine procedures and imaging associated with Y-90 therapy, including subjects who are pregnant or are planning to become pregnant, will not be eligible to participate in this study. Female subjects who are of childbearing potential should inform her treating physician should she become pregnant at any time during the course of the study.
2. Subjects with contraindications for receiving HIDA scans will not be eligible to participate in this study.

5. Patient Recruitment and Enrollment

Potential subjects will be patients with hepatocellular carcinoma who are planning to undergo Y-90 treatment at Indiana University Hospital. Potential subjects will be recruited through self-referral or the advice of their treating physician or clinical co-investigator on this study.

All patients who appear to be eligible for this trial will undergo the Informed Consent Process and be screened for eligibility. Eligible patients who complete the Informed Consent Process will be assigned a unique subject ID number and enrolled as a subject to this study. The subject will be given a copy of the signed, IRB-approved informed consent and HIPAA authorization documents, and the original signed informed consent and HIPAA authorization documents and regulatory files will be maintained by the Radiology Research Office. The process of obtaining consent (including date) must be clearly documented in the source documentation for this study. Applicable regulatory documents and approvals must be completed and on file prior to the enrollment of any subjects.

Subjects will be compensated for their time and effort with a \$25.00 gift card upon completion of each research imaging scan. A potential total of \$50.00 disbursed in gift cards per subject by the end of their participation in the study, if they undergo and complete the pre-Y90 HIDA and post-Y90 HIDA scan.

6. Study Procedures

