11.3 Analysis

Regional HIDA scan clearance rate results will be used for the primary analysis of the difference in regional liver failure between pre and 3 months post Y90 administration. Paired t-tests will be used. A similar method will be used for the global liver function difference. If the data is found to not be normally distributed, appropriate non-parametric tests will be performed for the comparisons. Spearman's correlation will be used to correlate the Y90 dose with the difference in regional and global liver function

12. Reporting Adverse Events

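### The Rationale wants the link between Y-90 and liver damage quantified, but the only dose analysis is a rank correlation, which gives no clearance loss per unit dose; a baseline-adjusted slope should be added beside it

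*Combined protocol and SAP*

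**What the plan says.** Section 2 (Rationale) sets the aim: "The primary question of interest is quantifying the relationship between Y-90 liver therapy and liver damage". It goes on to say that present Y-90 calculations are borrowed from surgery and external-beam radiation. It also describes estimating background-liver dose from the post-treatment PET/CT and combining it with HIDA function maps made before and after therapy. The background text before Section 2 hopes that the work will help to "develop a safer pre-treatment assessment model for avoidance of and prediction of REILD".

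The formal objectives are narrower. The primary objective (3.1) is: "Determine the difference in regional liver function between pre and 3 months post Yttrium 90 delivery using the HIDA functional imaging scans". Dose enters only in the second secondary objective (3.2): "Determine the correlation between the differences in liver function (both regional and global) with the Y 90 dose provided".

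Section 11.3 serves these objectives with two tools. For the change in regional and global function: "Paired t-tests will be used", with a non-parametric fallback. For dose: "Spearman's correlation will be used to correlate the Y90 dose with the difference in regional and global liver function". It specifies no regression, slope, covariate adjustment or confidence interval for any dose analysis.

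**The concern.** A rank correlation shows whether patients with more dose tend to lose more function, and how consistently. It does not show how much function is lost for a given increase in dose. If the Rationale is read as asking for a dose-response relationship, the final report could state that dose and loss are associated, but not what loss to expect at a given background-liver dose. The inputs for that estimate (PET/CT dose and the two HIDA scans) are already part of the study. Without a prespecified model, any slope reported later would come from a model chosen after seeing the data.

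**Working it through.** **1. Inputs.** From the documents: N = 50 (11.1); expected proportion 19% and 95% CI half-width 10.9% (11.2). The documents give no dose distribution, clearance SD, expected correlation or dropout rate. Assumed here: a correlation r between dose and change of 0.3, 0.4, 0.5 or 0.7, and 40 evaluable pairs as an alternative to 50.

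**2. The plan's own figure.** 1.96 × √(0.19 × 0.81 / 50) = 1.96 × 0.0555 = 0.109, so the 10.9% reproduces. It is the only precision figure in the plan. It concerns the incidence of clinical liver disease and has no bearing on the dose analysis.

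**3. Question set against method.**

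| Place | What is asked or done | Dose involved? | Loss per unit dose? |
|---|---|---|---|
| Section 2 | Quantify the therapy–damage relationship | Yes, by the surrounding text | Implied if dose-response is meant |
| Objective 3.1 | Regional change to 3 months | No | No |
| Objective 3.2, item 2 | Correlation of change with dose | Yes | Not asked |
| 11.3, paired t-test | Mean change in clearance | No | No |
| 11.3, Spearman | Rank association of dose and change | Yes | No |

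**4. What rho carries.** Without ties, rho = 1 − 6Σd²/[n(n² − 1)], where d is the difference between a patient's rank on dose and rank on loss. Multiplying every loss by a positive constant c leaves all ranks, and so rho, unchanged, while the least-squares slope is multiplied by c. Any increasing transformation of loss also leaves rho unchanged. Rho therefore holds no information on magnitude per unit dose or on the shape of the curve. This is a property of the statistic. It does not measure how much information this particular trial would lose.

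**5. What rho would deliver.** Using Fisher's z with variance (1 + r²/2)/(n − 3), at n = 50:
- Observed rho 0.3: z = 0.310, SE = √(1.045/47) = 0.149, 95% CI 0.02 to 0.54.
- Observed rho 0.5: z = 0.549, SE = √(1.125/47) = 0.155, 95% CI 0.24 to 0.69.

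**6. What a slope would deliver.** For a simple regression of change on dose, SE(b)/b = √[(1 − r²)/(n − 2)]/r. The 95% half-width as a share of the slope is t × √[(1 − r²)/(n − 2)]/r. At n = 50, t with 48 degrees of freedom is 2.011. For r = 0.5: 2.011 × √(0.75/48)/0.5 = 2.011 × 0.125/0.5 = 0.50.

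| Assumed r | n = 50 | n = 40 (assumed) |
|---|---|---|
| 0.3 | 92% | 104% |
| 0.4 | 66% | 75% |
| 0.5 | 50% | 57% |
| 0.7 | 30% | 34% |

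With baseline clearance as covariate, r becomes the partial correlation and one more degree of freedom is used, which changes little at this sample size. For r = 0.3: 2.012 × √(0.91/47)/0.3 = 93%. Robust standard errors could move these figures somewhat in either direction.

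**The case against.** The strongest reply is that the method matches the objective. The second secondary objective asks for a correlation, and 11.3 supplies one. The background text also speaks only of a potential correlation between background-liver dose and radioembolization-induced damage. Section 11.1 calls the study a pilot. All of this stands, and it means that the formal objectives and 11.3 agree with each other. The gap lies between them and the Rationale.

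A reader might go further and infer that the plan cannot answer its own primary question. The documents do not support that. The Section 2 sentence refers to therapy, not to loss per unit of absorbed dose, and the paired comparison does quantify the mean change after therapy in clearance units. Rho also quantifies something real: the direction and strength of a monotone association.

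A reader might also infer that a slope would itself provide the prediction model. The background text presents that model as a later product aimed at clinical liver damage, and 11.3 plans no such model. A clearance slope would inform that work without completing it.

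Finally, the imprecision seen in rho at n = 50 is shared by the slope, and nothing in the documents shows that a curvature check at this size could detect a threshold. Both points stand. They limit how the slope should be presented, but they do not remove the reason to report an effect size with its uncertainty.

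**Conclusion.** The point holds as a cheap improvement and does not expose a defect in the primary analysis. Neither analysis in 11.3 estimates clearance lost per unit of dose: Spearman's rho has no scale, and the paired t-test has no dose term. If the Rationale means a dose-response relationship, as its setting suggests, that estimate is missing although its inputs are to be collected.

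The gain should not be oversold. With all 50 patients evaluable, the 95% CI would extend about 92%, 66% or 50% of the slope on either side for correlations of 0.3, 0.4 or 0.5. With 40 pairs and r = 0.3 it would include zero (half-width 104%). The correlations and the 40 pairs are assumptions. The figures also presume a linear relation and ordinary standard errors.

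**What to change.** In 11.3, keep Spearman's rho, with a 95% CI, and add the following for regional and for global function, labelled as estimation only:

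- A linear regression of 3-month HIDA clearance on Y-90 dose, with baseline clearance as covariate. Use the PET/CT-derived background-liver dose described in Section 2 where available, and state the dose variable explicitly, because objective 3.2 refers only to the dose provided.
- The slope per fixed, prespecified dose increment, with a 95% CI from robust standard errors.
- Any check for curvature marked as exploratory, with no claim that it verifies linearity or rules out a threshold.

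Also align Section 2 with Section 3, so that it is clear whether the dose relationship is the primary question or a secondary one.

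The cost is a few lines of text and little analysis time, with no additional patients, scans or visits and no effect on clinical management. The downside is a linearity assumption and an imprecise slope. Presenting the result as estimation and retaining rho keeps both visible but does not remove them.

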6.1 Screening

Screening procedures to determine eligibility will include obtaining demographics and relevant medical history.

6.2 Pre Y-90 therapy

Each subject will undergo a HIDA scan after enrollment but prior to the initiation of Y-90 therapy for the purposes of this study. Additional imaging and laboratory tests will also be as part of routine clinical care prior to Y-90 therapy. These tests are the Tc99m MAA scan, CT scan, MELD/BCLC assessment and a blood serum chemistry test. The results of these tests will be collected for this study.

A HIDA scan involves the intravenous administration of a small amount of a radioactive tracer and imaging of the liver using a SPECT gamma camera. A 5 Mci dose of radioactive tracer mebrofenin (Tc99m bromo-2,4,6-trimethylacetanilido iminodiacetic acid) (HIDA) will be administered while the patient is on the imaging table. Images of the liver will be acquired for 30 minutes.

Whenever possible, the HIDA scan will be performed on the same day as the routine CT scan in order to use the intravenous access already placed for the CT imaging and minimize patient discomfort.

Adverse events will be assessed anytime procedures are being performed for research purposes only (i.e., HIDA).

6.3 Post Y-90 therapy

- At the time of Y-90 therapy, subjects will undergo a PET-CT scan to measure Yttrium distribution post-delivery of Y-90 per routine clinical practice.
- 3 months - Each subject will undergo a second HIDA scan approximately 3 months (+/- 30 days) after Y-90 therapy for the purposes of this study. Adverse event assessment will also be performed. Subjects will also have a CT scan and blood serum chemistry test as part of their routine clinical follow-up approximately 3 months (+/- 30 days) after Y-90 therapy, and the results of these tests will be collected for this study.
- 6 and 12 months - Subjects will have a CT scan and blood serum chemistry test as part of their routine clinical follow-up approximately 6 and 12 months (+/- 30 days) after Y-90 therapy, and the results of these tests will be collected for this study.

7. Study Calendar

	Pre Y-90 therapy		Y-90 Therapy	Post Y-90 Therapy		
	Screening	After enrollment but prior to Y-90 therapy		3 months	6 months	12 months
	Within 28 days of Y-90 therapy			+/- 30 days	+/- 30 days	+/- 30 days
Administration						
Informed consent	X					
Demographics	X					
Medical history	X					
Enrollment	X					
Adverse events assessment		X		X		
MELD/BCLC	X ³					
Routine Labs and Imaging Procedures						
Blood serum chemistry		X		X	X	X
Tc99m MAA scan		X				
CT scan		X		X	X	X
PET-CT			X ²			
Research Labs and Procedures						
HIDA scan ¹		X		X		

Footnotes:

¹ Whenever possible, the HIDA scan will be performed on the same day as the standard of care CT scan in order to use the intravenous access already placed for the CT imaging to minimize patient discomfort.

² At the time of Y-90 therapy, subjects will undergo a PET-CT scan to measure Yttrium distribution post Y-90 delivery per routine clinical practice.

³ MELD/BCLC will be collected per standard of care

8. Potential Risks and Procedures for Minimizing Risks

8.1 Risks Involved in a Hepatobiliary (HIDA) Scan

The risks involved in a HIDA scan are minimal. They include the following:

1. Radiation exposure; a very small amount of radioactive material is used and the radiation exposure is well below the level that causes adverse effects.
2. Allergic reactions to the radioactive material; however, this is extremely rare and without documented cases.

3. Discomfort, bruising or rash at the injection site or discomfort while lying on the table for the required amount of time for the scan. An effort will be made to schedule the HIDA scan at the same time as routine CT imaging in order to minimize discomfort.

8.2 Risks with Radiation

A very small amount of radioactive material is administered for the HIDA scan; therefore, subjects enrolled in this study will be exposed to radiation in addition to what is received as part of standard of care. The additional radiation exposure is well below the level that would cause adverse events. Please see table below for details regarding additional radiation exposure.

Administered Activity vs Dose Table:

	Administered activity		Largest radiation dose			Effective dose	
Radiopharmaceutical	MBq	mCi	Organ	mGy/MBq	rad/mCi	mSv/MBq	rem/mCi
^{99m} Tc-disofenin or ^{99m} Tc-mebrofenin	56–180 intravenously	1.5–5.0	Gallbladder wall	0.11	0.41	0.017	0.063

9. Potential Benefits

There will be no direct benefit to the patients participating in this study; however, one potential benefit of the study is the potential contribution to a greater understanding of the mechanisms of liver functioning and safety in radioembolization therapy with Y-90 for hepatocellular carcinoma.

10. Criteria for Removal from Study

Every subject should be encouraged to remain in the study. Possible reasons for early withdrawal may include, but are not limited to, the following:

1. Withdrawal of consent – Subject decides to withdraw from the study. This decision must be an “independent decision” that is documented in the source documentation.
2. Principal Investigator and/or treating physician discretion – The Principal Investigator and/or treating physician may choose to withdraw a subject from the study if there are safety or other concerns.
3. Subject’s treatment plan for Y-90 therapy is cancelled.

4. Subject's treatment location for Y-90 therapy is moved to another institution outside of Indiana University Health Hospital.
5. Subject becomes pregnant.
6. Subject has contraindication to HIDA scan that is discovered after enrollment.
7. Subject non-compliance.
8. Subject lost to follow-up.
9. Subject death.

11. Statistical Considerations

